6 ASSESSMENT PLAN

6.1 Schedule of Assessments

Stage	Screening	Baseline	On study treatment	At First Progression (PSA or radiological) ¹ AND End of Treatment for reasons other than progression	After last dose of study treatment		
Timing	Within 28 days prior to randomisation	Within 7 days prior to randomisation	All participants Day 15, then 4 weekly (\pm 7 days) ⁸	\pm 7 days	42 days and 84 days after last dose of study treatment (\pm 7 days)	Until radiological progression (6 weekly \pm 7 days)	After radiological progression (12 weekly \pm 7 days)
Informed consent (including Medicare consent)	X						
Medical oncology assessment ²	X	X ⁹	X	X	X	X	
Blood tests ³	X	X ⁹	X	X	X	X	
PSA	X	X ⁹	X	X	X	X	
Translational research bloods ^{4a}		X ^{4b}	Day 92 only	At first progression only, before subsequent therapy ⁵			
⁶⁸ Ga-PSMA PET/CT	X		Days 15 and 92	X (At progression only) ⁵			
¹⁸ F FDG PET/CT	X			X (At progression only) ⁵			
SPECT CT			24hrs post Lu-PSMA				
CT CAP / Whole body bone scan ⁶	X		Day 99, then 12 weekly thereafter	X		12 weekly until radiological progression	
Tissue biopsy ^{4a}		Optional ^{4c}		Optional (At progression only) ⁵			
Adverse events ⁷			X	X	X		
Compliance			Days 15 and 43				
Concomitant medications				Within 30 days prior to an SAE			
HRQL forms		X ¹⁰	X (not day 15)	X	X	X	
Fear of Cancer Progression Short Form		X ¹⁰					
Survival and Subsequent Treatment					X	X	X

Notes

1. Refer to section 7.1 for definition of PSA progression or 7.2 for definition of Radiological progression.
2. Clinical assessment includes history (at baseline) and physical examination, performance status and weight. All visits after baseline include a review of any adverse events and physical examination as per standard of care for a participant at this stage of their disease and treatment
3. Blood tests include the following:
 - Haematology: Complete blood examination (CBE): haemoglobin concentration, white cell count, platelet count, white cell differential.
 - Biochemistry: Electrolytes, urea, creatinine (EUC); liver function tests (LFT): bilirubin, alkaline phosphatase (ALP), alanine aminotransferase (ALT), gamma glutamyl transferase (GGT), lactate dehydrogenase (LDH; screening only)
4. a. Refer to Biological Sampling Manual for details of collection, processing and shipping procedures.
b. Baseline TR blood draw after randomisation, within 7 days prior to commencing study treatment.
c. Baseline tissue biopsy (optional) may occur any time after patient consents (pre- or post-randomisation), but prior to commencing study treatment. Refer to the Biospecimen Sampling Manual for details.
5. PSA progression and radiological progression may occur at different times. If so, then ⁶⁸Ga-PSMA PET/CT, ¹⁸F FDG PET/CT, translational research blood collection and tissue biopsies (optional) are only required to be completed at first documented progression (either PSA or radiological, whichever occurs first).
6. Imaging must include a CT of the chest, abdomen and pelvis, and a radio-isotope whole body bone scan (WBBS). If screening FDG PET imaging includes a diagnostic CT, then a separate baseline CT is not required. 12-weekly imaging with CT and WBBS should continue until radiological progression is documented per RECIST 1.1 or PCWG3 (see section 7.2), even if new anticancer treatment is commenced earlier.
7. Adverse events categorised and graded according to CTCAE v5.0 and should continue to be recorded until 12 weeks after the study treatment ends.
8. For Day 15 assessments a window of +7 days only is permitted, with the exception of the Day 15 ⁶⁸Ga-PSMA PET which has a -5/+7 day window
9. If screening medical oncologist assessment, blood tests and PSA were completed within 7 days prior to randomisation, then they do not need to be repeated.
10. Baseline HRQL forms and Fear of Cancer Progression Short Form can be completed within 7 days pre- or post-randomisation, prior to commencing study treatment.

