1.7 Tumour Heterogeneity

A key challenge to the development of any personalized therapies is the intrinsic dynamism of multiple tumour clones that can evolve and acquire resistance with pressure selection. While the PSMA receptor is highly expressed in prostate cancer, with increasing expression in metastatic disease and with more aggressive tumour types, the expression of PSMA in prostate cancers is heterogeneous, particularly at the later stages of the disease. A study that assessed both primary and metastatic prostate cancer samples found that only 4% (2/51) primary tumours were PSMA negative, while 16% (8/51) of metastatic samples were PSMA negative or had low expression (42). An assessment of PSMA expression in circulating tumour cells (CTCs) from men with metastatic disease found significant variation in the ratio of PSMA positive and PSMA negative CTC levels between patients (43). This heterogeneity of PSMA expression has direct implications for the use of PSMA targeted therapy, and in the development of PSMA targeted therapy resistance. Recent work has shown that high uptake on PSMA PET is an important consideration for selecting men suitable for ¹⁷⁷Lu-PSMA therapy: between 15-30% of men will not be eligible for PSMA targeted treatment due to PSMA low or negative receptor expression. In the prospective study of Lu-PSMA undertaken at St Vincent's Hospital, Sydney, men who failed Lu-PSMA therapy had lower PSMA avidity on

screening images. No one with an SUV <15 on screening PSMA PET had a treatment response to Lu-PSMA therapy (6). This is an important consideration for Lu-PSMA therapy, especially if considering a therapy move to earlier stages of the prostate cancer journey, where PSMA intensity is often lower (it upregulates in castrate resistant disease). Hence, the concept of combining Lu-PSMA therapy with a therapeutic agent that also upregulates the PSMA receptor, is appealing. Early animal work has shown that incubating LNCaP cells with enzalutamide and lutetium-PSMA increases the lutetium entry into the cell more than incubating with Lu-PSMA alone (41).

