4.4.2 Registration for ^{68}Ga -PSMA PET/CT

For registration to this study, potential participants must meet all of the eligibility criteria except those relating to imaging with ^{68}Ga -PSMA PET/CT (inclusion 6 and exclusion 2).

After participants are registered for the study, imaging with ^{68}Ga -PSMA PET/CT and FDG PET/CT will be performed. These procedures including manufacture of ^{68}Ga -PSMA are according to the Imaging Manual. The images will be completed at participating sites, and sent electronically in DICOM format to a central repository. The images will be centrally reviewed within 3 working days to determine eligibility for randomisation. Reason(s) for ineligibility will be recorded.

Participants who have provided consent but do not meet all the eligibility criteria will be recorded as screen failures.

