6.2.4 Tissue Collection

Where available, archival formalin-fixed paraffin-embedded (FFPE) tumour tissue will be retrieved from all patients and may be used for translational research studies.

Additional tumour biopsy will be undertaken at baseline and at first progression in participants consenting to biopsies in the trial. This baseline biopsy will be guided by the screening ⁶⁸Ga-PSMA PET/CT result. Core biopsies will be obtained. Refer to the Biospecimen Sampling Manual for details including processing of fresh tissue (e.g. in media, RNAlater) where relevant.

The first progression (PSA or radiological) biopsy will be guided by molecular imaging at first progression (⁶⁸Ga-PSMA PET/CT and ¹⁸F-FDG PET) and will target sites of metabolic tumour progression (these sites may be PSMA avid or FDG avid, but not negative on both PET images, unless a site of clear progression and tumour involvement by RECIST criteria on the diagnostic CT scan). Refer to the Biospecimen Sampling Manual for details including processing of fresh tissue (e.g. in media, RNAlater) where relevant.

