8.2 Recording Adverse Events

AEs will be recorded from the first dose of study treatment until 12 weeks after cessation of study treatment. The CTCAE v5.0 will be used to classify and grade the intensity of AEs after each treatment cycle. The worst grade will be recorded for each event. The investigator's assessment of attribution to study drug administration will also be collected.

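### Note 4c on baseline biopsy timing conflicts with section 6.2.4 and allows biopsy before PSMA eligibility is confirmed, and the biopsy's non-serious complications fall outside adverse event recording

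*Protocol*

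**What the plan says.** Four parts of the protocol bear on this point.

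- **Biopsy timing (6.1, note 4c).** "Baseline tissue biopsy (optional) may occur any time after patient consents (pre- or post-randomisation), but prior to commencing study treatment". The table places the optional biopsy in the Baseline column.
- **Biopsy guidance (6.2.4).** "This baseline biopsy will be guided by the screening ⁶⁸Ga-PSMA PET/CT result". The biopsy at first progression is likewise guided by PET.
- **Enrolment order (4.4.1 to 4.4.3).** Consent precedes any study-specific screening. The PSMA PET/CT follows registration, and of that scan the protocol says: "The images will be centrally reviewed within 3 working days to determine eligibility for randomisation". Consented men who do not qualify are handled thus: "Participants who have provided consent but do not meet all the eligibility criteria will be recorded as screen failures".
- **Safety recording (8.1 to 8.3 and the AE row of 6.1).** "AEs will be recorded from the first dose of study treatment until 12 weeks after cessation of study treatment". The AE row has no entry under Screening or Baseline. Section 8.3 requires all SAEs during the study to be reported. It states when this duty ends but not when it begins. The AE definition in 8.1 refers to a person who has been given a pharmaceutical product.

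**The concern.** The baseline biopsy is an invasive procedure done for research only. Two things follow from how its timing is written.

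First, a site that reads note 4c alone may schedule the biopsy as soon as consent is signed, while a site that reads 6.2.4 must wait for the scan. Neither passage requires central review to be complete. A man can therefore be biopsied and then be found ineligible on PSMA avidity. He would contribute nothing to the randomised comparison and would have no on-study progression sample to pair with his baseline tissue.

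Second, the period in which the biopsy may be done and the period in which AEs are recorded do not overlap. A non-serious complication such as minor bleeding or pain has no place in the trial's AE data, whether or not the man is later randomised.

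**Working it through.** The protocol gives no figure on this point to reproduce. The check is to set the time windows side by side.

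**Order of events, from 4.4.1 to 4.4.3 and 6.1**

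1. Consent.
2. Registration.
3. Screening PSMA PET/CT.
4. Central review, within 3 working days.
5. Randomisation.
6. Start of enzalutamide, planned within 7 days after randomisation.

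**Biopsy window**

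- Note 4c: from step 1 to just before step 6.
- Section 6.2.4: from step 3 (the scan result must exist) to just before step 6.
- The two differ over steps 1 to 3. That is the contradiction.
- Under either reading the window includes the time between steps 3 and 4, before eligibility on PSMA avidity is settled.

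**AE window**

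- Section 8.2: opens at step 6.
- The biopsy window closes before step 6, so the overlap is nil. This holds for biopsies after randomisation as well as before it.

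**SAE window**

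- Section 8.3: no start is stated. The end is 12 weeks after Lu-PSMA or 30 days after the last enzalutamide dose, whichever is first.
- A man who is never treated has neither end date.
- The wording about SAEs during the study may cover a serious biopsy complication after consent. The definition in 8.1, tied to administration of a product, points the other way. The text does not settle it.

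**Scale, for illustration only**

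Section 1.7 says that "between 15-30% of men will not be eligible for PSMA targeted treatment due to PSMA low or negative receptor expression". Assume, without support in the protocol, that this share *f* applies to men scanned in this trial. Section 13.1 gives 160 randomised. Counting PET failures only:

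- Men scanned = 160 / (1 − *f*).
- *f* = 0.15: 160 / 0.85 = 188.2, so 189 scanned and 189 − 160 = 29 PET failures.
- *f* = 0.30: 160 / 0.70 = 228.6, so 229 scanned and 229 − 160 = 69 PET failures.

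The number of these men actually biopsied equals the PET failures multiplied by the share who accept the optional biopsy and have it before central review reports. The protocol does not give that share. The answer therefore lies anywhere from 0 to the full 29 to 69, and no point estimate is justified.

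**The case against.** The strongest reply is that note 4c should be read with 6.2.4. The note uses permissive language and sets outer limits, while 6.2.4 is a firm requirement. Read together, the biopsy falls after the scan and before treatment. That stands to this extent: a reader might infer that the protocol deliberately allows untargeted biopsies before the PET, or that baseline tissue will not be comparable with progression tissue. Both would need a site to depart from 6.2.4. What remains is a conflict in wording, and harmonising the note with 6.2.4 alone would still leave the gap before central review. Both passages refer to the Biospecimen Sampling Manual for details. It is not shown and may settle the timing, but a manual does not remove two conflicting statements in the protocol.

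A reader might also infer that all biopsy complications go unrecorded. The documents do not support that. Section 8.3 has no start at first dose, 8.1 mentions SAEs associated with trial procedures among its examples of safety issues, and 15.4 asks for AEs to be entered in the medical record. The firm gap is confined to non-serious events as trial AE data.

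Two further inferences fail. The 15-30% cannot be read as the share of biopsies wasted, since it is background on PSMA-targeted treatment in general and not a forecast under this trial's uptake thresholds. Nor can it be said that the safety committee is deprived of data: 14.3 refers to a charter that is not shown.

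Finally, taking tissue before allocation is a reasonable choice in an open-label trial, because acceptance then cannot depend on the arm. That stands, and the fix keeps it.

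**Conclusion.** The point holds in three parts:

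- Note 4c and 6.2.4 contradict each other on when the baseline biopsy may first be done.
- The protocol allows an optional research biopsy before central review has confirmed PSMA eligibility, so some biopsied men may become screen failures. How many cannot be derived.
- Every baseline biopsy precedes the start of AE recording, so its non-serious complications are not recorded as trial AEs. Serious ones are arguably reportable, but the text leaves this open.

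This rests on the protocol's wording alone, with the Biospecimen Sampling Manual and the safety committee's charter unseen. The matter concerns participant protection and completeness of procedure-related safety data. The sample size, the primary endpoint and its analysis are untouched, and the section 13.2 safety comparison covers treated, randomised men only. It is worth correcting because the correction is small.

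**What to change.** 1. **Note 4c and 6.2.4.** Open the biopsy window once central review of the screening PSMA PET/CT has confirmed PSMA eligibility. Keep the rest: before or after randomisation, and before study treatment. State it identically in both places and check the Biospecimen Sampling Manual against it.
2. **8.2, 8.3 and the AE row of 6.1.** State that AEs and SAEs related to study procedures, including the biopsy, are recorded from consent and also in screen failures. All other AEs stay from the first dose. Give an end to this recording for men who are never treated, and make clear that the definition in 8.1 does not exclude them.

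The first change reduces biopsies in men never randomised but does not remove them, because 4.4.3 requires all criteria still to be met at randomisation and a man can fail after a favourable scan.

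The cost is a short amendment, a slightly shorter interval in which to book the biopsy, and a little more AE recording. The interval stays workable: central review is due within 3 working days, and the biopsy can still be done after randomisation until treatment starts, which is planned within 7 days.

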3 DESIGN

Randomised, phase 2, stratified, multicentre, open label clinical trial.

Participants will be randomised to enzalutamide or enzalutamide and Lu-PSMA in a 1:1 ratio. A minimisation approach will be used to minimise chance imbalances across the following stratification factors: study site, volume of disease (>20 versus ≤ 20 sites of disease measured on ^{68}Ga -PSMA PET/CT), prior treatment with early docetaxel for castration-sensitive disease (yes vs no), and prior treatment with abiraterone (yes vs no).

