4.4.3 Randomisation

Participants must continue to meet all of the inclusion criteria and none of the exclusion criteria to be randomised in this study. Participants will be randomly allocated (1:1) to treatment with either enzalutamide, or Lu-PSMA and enzalutamide.

If screening bloods were collected within 7 days prior to randomisation, baseline bloods do not need to be repeated.

Enzalutamide should be planned to start within 7 days after randomisation and Lu-PSMA within 21 days after randomisation. Randomisation will be done according to the instructions in the Study Manual. Once the randomisation process has been completed, the participant will be assigned a treatment group. Confirmation of each randomisation will be provided to the site. Individuals may only be randomised once in this trial.

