6.2.5 Aspects of health-related quality of life

McGill-Melzack Present Pain Intensity Scale, the EORTC QLQ-C30 and Patient Disease and Treatment Assessment Form will be completed every 4-6 weeks until radiographic progression (see schedule of assessments). The Fear of cancer progression short form will be completed at baseline only.

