7.4 Pain response and Progression-Free Survival (PPI)

Pain is measured using the McGill-Melzack Present Pain Intensity scale (PPI, see Appendix 4).

Pain Response is defined as a reduction of 2 or more points for participants with a baseline PPI score of ≥ 2 .

Pain progression is defined as and an increase of 1 or more points in the nadir PPI score.

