13.2 Statistical Analysis

A statistical analysis plan will be finalised prior to data-lock, and contain additional detail on the methods described below.

All randomised participants will be eligible for inclusion in the full analysis set in accordance with the intention-to-treat analysis principle. Analysis of efficacy endpoints will be undertaken on participants in the full analysis set. A sensitivity analysis using a per-protocol analysis set may be performed on efficacy endpoints. The safety population will comprise all randomised participants who received at least one administration of study medication. Participants will be analysed according to the regimen they actually received for the purposes of the safety analysis.

All p-values and confidence intervals will be two-sided.

The primary analysis will be a comparison of PSA PFS in the two treatment arms using a log-rank test accounting for clinical stratification factors. Kaplan-Meier curves for PSA PFS will also be prepared. An estimate of the hazard ratio will be obtained using Cox proportional hazard regression accounting for clinical stratification factors. Other time-to-event endpoints will be analysed in a comparable fashion to the primary endpoint.

Treatment groups will be compared on binary endpoints (e.g. PSA response) using a Cochran–Mantel–Haenszel χ^2 test accounting for the clinical stratification factors. Multivariable logistic regression will be used to estimate odds ratios with confidence intervals for covariates and assigned treatment.

Scale scores from the QLQ-C30 and PDF will be summarised by group over time. The applicability of repeated measures mixed modelling to these scales will be investigated. This will involve fitting a linear mixed model with patient as the random effect, and fixed effect terms for treatment allocation, time point, a time point-by-treatment allocation interaction, and the baseline assessment.

The analysis of safety data will be principally descriptive in nature. Adverse Events (AEs) and Serious Adverse Events (SAEs) will be tabulated by treatment allocation and CTCAE v5.0 criteria including system organ class, term, and worst grade.

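### Baseline quality-of-life forms may be completed after open-label randomisation, so some of the baselines used for adjustment, and probably for pain response, may be answered with the allocation known

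*Protocol*

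**What the plan says.** The baseline column of the schedule in Protocol section 6.1 is set in the week before randomisation. Note 10 makes an exception for the patient-reported forms: "Baseline HRQL forms and Fear of Cancer Progression Short Form can be completed within 7 days pre- or post-randomisation, prior to commencing study treatment".

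Section 3 describes the trial as "Randomised, phase 2, stratified, multicentre, open label clinical trial". On disclosure of the arm, section 4.4.3 says "Confirmation of each randomisation will be provided to the site". On timing of treatment it says "Enzalutamide should be planned to start within 7 days after randomisation and Lu-PSMA within 21 days after randomisation".

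The baseline is used in two places:

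- Section 13.2 proposes a linear mixed model for the QLQ-C30 and PDF scales, with "fixed effect terms for treatment allocation, time point, a time point-by-treatment allocation interaction, and the baseline assessment".
- Section 7.4 says "Pain Response is defined as a reduction of 2 or more points for participants with a baseline PPI score of" 2 or more.

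Section 6.2.5, on health-related quality of life, groups the pain scale (PPI) with the other forms: "McGill-Melzack Present Pain Intensity Scale, the EORTC QLQ-C30 and Patient Disease and Treatment Assessment Form will be completed every 4-6 weeks". The same section has the fear-of-progression form completed once, at baseline.

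**The concern.** A baseline covariate is safe to adjust for because randomisation cannot have influenced it. That protection is lost if it is measured after the arm is disclosed. Many of the items are subjective (worry, tension, overall quality of life, the thought of having treatment) and could plausibly move when a man learns whether he will receive the radioligand.

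If the average baseline moves differently in the two arms, the adjusted comparison carries part of that movement as apparent treatment effect. It could go either way. Disappointment in the enzalutamide-alone arm would worsen that arm's baseline and make its later course look better. Apprehension in the combination arm would do the reverse.

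For pain response, a shifted baseline would change both who enters the denominator and the score from which a fall is counted.

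**Working it through.** No figure in the protocol depends on this point, so there is none to reproduce. The check is whether the window is real, then how large the effect could be.

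**Is the window real?** Forms may be completed up to 7 days after randomisation, before treatment. Enzalutamide may start up to 7 days after randomisation. The two intervals coincide, so up to a week can pass in which the arm is known, treatment has not begun and the form still counts as baseline. The protocol says that the site is told the allocation. It does not say when the man is told, and nothing holds this back until the forms are done.

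**Adjusted HRQL contrast.** Let p be the share of one arm's forms completed late, s the shift among those forms, and b the slope of follow-up on baseline. The arm's mean baseline moves by p x s, and the adjusted contrast for that arm moves by about

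bias = -(p x b x s).

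Only the difference between arms matters; an equal shift in both cancels. None of p, b and s is in the protocol. Assuming b = 0.5 to 0.6 on a 0-100 scale, the absolute bias in points is:

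| Share late in one arm | Shift of 5 points | Shift of 10 points |
|---|---|---|
| 20% | 0.2 x (0.5 to 0.6) x 5 = 0.5 to 0.6 | 1.0 to 1.2 |
| 50% | 1.25 to 1.5 | 2.5 to 3.0 |
| 100% | 2.5 to 3.0 | 5.0 to 6.0 |

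A simulated analysis of covariance agrees with the formula. It used one follow-up value, 80 men per arm (160 randomised 1:1), no true effect and a two-sided 5% test, with baseline-to-follow-up correlations of 0.3, 0.5 and 0.7:

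| Shift in one arm's mean baseline | Absolute bias (SD) | False-positive rate |
|---|---|---|
| 0 | about 0 | about 5% |
| 0.1 SD | 0.03 to 0.07 | 5% to 9% |
| 0.2 SD | 0.06 to 0.14 | 7% to 23% |
| 0.3 SD | 0.10 to 0.21 | 10% to 45% |

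These are shifts of the whole arm's mean. If 20% of forms are late and each moves by 0.5 SD, the arm mean moves by 0.2 x 0.5 = 0.1 SD, which is the second row.

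**Pain response, if the PPI falls under note 10.** A man whose true score is 1 but who reports 2 becomes evaluable, and he counts as a responder if he later reports 0, although his true fall is 1 point. For illustration, assume baseline scores 0 to 5 in proportions 30, 30, 20, 12, 6 and 2%. Assume true changes of -2, -1, 0 and +1 in proportions 20, 30, 35 and 15%, the same in both arms. Let a share q of one arm report one point more at baseline:

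| q | Evaluable | Apparent response |
|---|---|---|
| 0 | 40% | 20% |
| 10% | 43% | 25% |
| 20% | 46% | 29% |
| 30% | 49% | 32% |

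Here q is the share late multiplied by the share of late men who move a full point. If 20% are late and half of them move, q is 10%.

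**The case against.** A reader might infer that every post-baseline contrast is biased by 2.5 to 3 points, or that all patient-reported secondary endpoints are compromised. The document supports neither.

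- **Size.** The 2.5 to 3 points require a whole arm's mean to shift by 5. Note 10 permits late forms but does not require them, and the baseline column still points to the week before randomisation. The true figure could be near zero.
- **PPI.** Note 10 does not name the PPI. Section 6.2.5 groups it with the HRQL forms and the schedule has no separate PPI row, but section 7.6 omits it from its list of HRQL instruments. The pain-response part is therefore an inference.
- **Pain progression.** Section 7.4 measures this from the nadir and does not say that baseline counts towards it. Exposure there is a further inference.
- **Fear form.** It is collected once, so it has no post-baseline contrast to bias.
- **Mixed model.** Section 13.2 says only that its applicability will be looked into; the firm commitment is a summary by group over time.
- **Recall.** The PPI covers the last 7 days, most of the QLQ-C30 the past week, and the PDF 3 weeks or a month. A form completed soon after randomisation mostly describes time before it. This dampens a shift but does not rule it out.
- **Follow-up.** All later forms are answered knowing the arm, so open-label reporting bias remains whatever is done about baseline.

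These points limit the size and reach of the concern; they do not remove it. The timing rule is fixed in the protocol, and an analysis plan cannot recover a baseline that was never taken before randomisation.

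It could also be said that no pre-randomisation visit need exist, because note 9 waives the repeat assessments. That fails: the waiver applies only when the screening assessment, bloods and PSA were themselves done in the 7 days before randomisation, so a contact always falls in that week.

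**Conclusion.** The point holds in limited form. Note 10 allows baseline patient-reported forms to be completed after the arm is known, and that baseline is a covariate in the proposed QLQ-C30 and PDF model. If the PPI is collected with those forms, it is also the filter and the reference for pain response.

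With an assumed slope of 0.5 to 0.6 and an assumed 5-point shift in one arm, the bias is about 0.5 to 0.6 points when 20% of that arm's forms are late, rising to 2.5 to 3 points only when all are. The protocol gives no share, shift or direction, so it shows that bias is possible, not that it will occur or whom it would favour. PSA progression-free survival and the other endpoints that are not patient-reported are unaffected. This is a cheap improvement to the secondary patient-reported outcomes, not a threat to the trial's main conclusion.

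**What to change.** Change note 10 so that the baseline HRQL, PPI and fear-of-progression forms are completed within 7 days before randomisation, and name the PPI explicitly. They can be done at the contact where the clinical assessment, bloods and PSA are taken: the baseline visit, or screening if that falls within the 7 days.

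Record each form's completion date so that it can be compared with the date of randomisation; the forms in Appendices 5 to 7 already have a date field. For any form completed after randomisation, run a sensitivity analysis that does not use it as baseline. This part remains possible if forms have already been collected under the present note.

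The cost is one footnote, a date check and a few baseline forms missed where a site overlooks them before randomisation. Men whose late form is set aside lack a baseline covariate and a pain-response reference in that analysis, which is why it should be a sensitivity analysis. No sample-size figure changes.
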